5.12.5 Puffing topography measurements

At clinic visits at the end of Weeks -1, 2 and 6, a randomly-selected subset of 18 non-menthol and 18 menthol smoker subjects will complete a puffing topography evaluation session with either their UB (Week -1) or the VLN (Weeks 2 and 6) cigarettes. These subjects will be/have been assigned to switch to smoking VLN cigarettes. These assessments will only be performed at a single clinical site (Lincoln) and will take place during the 24-hour confinement period.

During the puffing topography assessment, subjects will engage in a 1-hour *ad libitum* smoking session with their UB (Week -1) or the VLN (Weeks 2 and 6) cigarettes. In these sessions, subjects will smoke cigarettes with the mobile smoking puff analyzer (SPA-M; Sodim). The topography device will be monitored to ensure the device is actively recording during each session.

Topography assessment will be started at least one hour following either the subject's breakfast or lunch. The puffing topography session for each subject at Weeks 2 and 6 should be within \pm 2 hours of the time of their Week -1 session.

Additional details and instructions for puffing topography procedures will be provided separately.

The following topography parameters will be assessed:

- Puff duration
- Puff volume
- Peak puff flow rate
- Average flow rate
- Inter-puff interval

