3. STUDY DESIGN

This is an open-label, randomized, forced-switching study to be conducted at multiple study sites. Seventy (70) self-affirmed exclusive filtered non-mentholated cigarette smokers and 70 self-affirmed exclusive filtered mentholated cigarette smokers will be enrolled and begin the study at Week -1.

All potential subjects will provide informed consent and successfully complete the Screening procedures prior to participation in the study. Subjects will also engage in a

brief product trial with the VLN cigarettes. Subjects who react negatively (i.e., unwilling to use and/or cannot tolerate the product [experience AEs that will prevent them from continuing to use the product as judged by the Investigator]) to the VLN cigarettes during the product trial period will not continue in the study.

At the start of Week -1, all subjects will be asked to smoke their UB cigarettes as per their usual daily consumption for the following week. Subjects will receive an e-diary to record daily cigarette use (CPD). Training in completion of the e-diary will be provided at the visit at the start of Week -1.

Subjects will return at the end of Week -1, at the time indicated by the clinical research unit (CRU), for collection of blood and 24-hour urine samples for baseline BoE assessments. Subjective questionnaires for dependence, withdrawal symptoms, urges to smoke, and perceived health risk will also be completed at scheduled times. A randomly-selected subset of 18 non-menthol and 18 menthol smoker subjects will complete an assessment of puffing topography with their UB cigarettes during this visit. A further subset of 12 of the non-menthol and 12 of the menthol smoker subjects who complete the topography assessment will also complete a nicotine PK assessment at the end of this visit. Subjects who undergo topography and PK assessments will be assigned to switch to smoking VLN cigarettes.

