On Day -1 of Week 1, subjects will be randomly selected to either remain smoking their non-menthol (20 subjects) or menthol (20 subjects) UB cigarettes, or to switch to smoking non-menthol (50 subjects) or menthol (50 subjects) VLN cigarettes as per their UB cigarette flavor. Subjects will return at the end of Weeks 2 and 6, at the time indicated by the CRU, for collection of blood and 24-hour urine samples for BoE assessments. Subjective effects questionnaires will also be completed at scheduled times. Subjects will continue recording their CPD in their e-diaries. The same subset of 18 non-menthol and 18 menthol smoker subjects selected to complete a puffing topography assessment with their UB cigarette on Week-1, will complete an assessment of puffing topography with the VLN cigarettes at these visits, and a further subset of 12 non-menthol and 12 menthol smoker subjects will also complete an assessment of nicotine PK at the end of these visits. Subjects undergoing topography and PK assessments will have been assigned to switch to smoking VLN cigarettes.

Additionally, all subjects will visit the clinic at the end of Week 4 to receive further supplies of cigarettes (if assigned to the VLN groups) and to complete subjective effects questionnaires.

Subjects randomized to the VLN groups will be provided with a supply of VLN cigarettes at each visit, which will be 150 % of their usual daily consumption as reported during Week 1. If a subject runs out of cigarettes between clinic visits, they may visit the clinic to receive additional test cigarettes. All subjects will be asked to smoke their cigarettes *ad libitum*, recording their actual daily consumption in their e-diaries. Non-compliant nicotine product consumption should also be recorded. Used

cigarette butts will also be collected during ambulatory periods to verify product use and/or assess compliance. During Week 1 (all subjects) and all subsequent weeks (subjects randomized to continue smoking UB cigarettes) subjects will be asked not to change their UB cigarette brand or flavor.

The CRU will attempt to contact all subjects who participated in the study (including subjects who terminate the study early) using their standard procedures approximately 7 days after the last contact to determine if any AE has occurred since the last study visit.

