7.3 Statistical Analysis of Primary Endpoints

Paired t-tests will be used to compare cigarette consumption (CPD) and puffing topography parameters at the Week 2 and Week 6 time points with the baseline (Week -1) values. This analysis will be conducted on the evaluable subjects in the PP population. If data are unexpectedly found not to be normally distributed, an appropriate non-parametric test will be performed. Differences will be considered statistically significant at an alpha level of 0.05. Means, difference of means, 90% confidence interval for difference, and p-value will be presented.

The following SAS codes will be used for the analysis:

```
Proc ttest data=<>;  
By product_group;  
Paired week_X*baseline;  
Run;
```

Where week_X will be either Week 2 or Week 6. Product Groups are VLN non-mentholated, VLN non-mentholated, and VLN combined which pooled non-mentholated and mentholated groups. The primary analysis will be based on the VLN combined product group.

In addition, a linear mixed model analysis of variance will be used to compare the between product group differences in the absolute change from baseline values of the consumption and puffing topography parameters. Product group, week, and product group by week interaction will be the fixed factors in the model. A restricted maximum likelihood estimation method with an unstructured (UN) covariance structure will be applied. If the model does not converge, the first order autoregressive AR(1) and/or compound symmetry CS covariance structures will be tested as alternatives. The least-square mean difference, 95% confidence interval and p-value will be provided for the product group difference. The pairwise comparisons (VLN non-mentholated versus UB non-mentholated, VLN mentholated versus UB mentholated, and VLN combined versus UB combined) will be performed at week Week 2 and Week 6. Least-square means (LSMeans), difference of LSMeans, 90% confidence interval for difference, and p-value for difference will be presented.

The following SAS codes will be used to perform the analysis.

```
Proc mixed data=<>;  
Class subject product_group week;  
Model response = product_group week product_group*week /ddf=kr;  
Repeated week/type=<type> subject=subject;  
LSmeans product_group*week/CL alpha=0.05 CL pdiff;  
Run;
```

The primary analysis will be the pairwise comparisons of VLN combined versus UB combined (pooled non-mentholated and mentholated groups).

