14.2.3 Puff Topography Parameter Tables

Table 14.2.3.1.1 Summary of Puff Topography Parameters by Study Product Group and Study Week (PP Population)

Table 14.2.3.1.2 Summary of Puff Topography Parameters by Study Product Group and Study Week (ITT Population)

Table 14.2.3.2 Statistical Comparison of Puff Topography Parameters at Weeks 2 and 6 Versus Week -1 by Study Product Group (PP Population)

Table 14.2.3.3 Statistical Comparison of Puff Topography Parameters Among Study Product Groups at Weeks 2 and 6 (PP Population)

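### SAP 7.3 applies VLN-versus-UB contrasts, one labelled primary, to puffing topography, which is measured only in VLN subjects; the paired test that remains has no rule for concluding no change

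*SAP*

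**What the plan says.** **Who has topography data.** Protocol 5.12.5 and SAP 7.1.3 describe a subset of 18 non-menthol and 18 menthol smokers at one site: "These subjects will be/have been assigned to switch to smoking VLN cigarettes". SAP 3 says so twice: "Subjects who undergo topography and PK assessments will be assigned to switch to smoking VLN cigarettes" and "Subjects undergoing topography and PK assessments will have been assigned to switch to smoking VLN cigarettes". The subset smokes UB at Week -1 and VLN at Weeks 2 and 6.

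**What is planned.** SAP 7.3 sets out two analyses for both consumption and topography.
- The first is a paired t-test of Weeks 2 and 6 against Week -1 in the per-protocol population, at alpha 0.05. Of this it says "The primary analysis will be based on the VLN combined product group" and "Means, difference of means, 90% confidence interval for difference, and p-value will be presented".
- The second is a mixed model of "between product group differences in the absolute change from baseline values of the consumption and puffing topography parameters", with three contrasts at each of Weeks 2 and 6: VLN against UB in non-menthol smokers, in menthol smokers, and pooled. The section closes with "The primary analysis will be the pairwise comparisons of VLN combined versus UB combined (pooled non-mentholated and mentholated groups".

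The planned outputs include "Table 14.2.3.3 Statistical Comparison of Puff Topography Parameters Among Study Product Groups at Weeks 2 and 6 (PP Population", whose shell contains only those three contrasts.

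**What is expected.** Protocol 1.3 and SAP 2.2 anticipate that topography will not change, meaning no compensation. Protocol 6.1.2 and SAP 4.2 size topography at 12 per VLN group for a two-tailed paired t-test with 80% power to detect differences.

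**The concern.** A contrast labelled primary, on an endpoint that belongs to the primary objective, has no data on one side. SAP 5.1 sends the topography tables listed in SAP 13 into the topline reports, so an unfillable table is scheduled for an early deliverable, and the programmer would have to improvise a replacement after data are available.

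The analysis that can be run does not match the hypothesis. A difference test at 0.05 can show that topography changed. It cannot show that it did not, unless the interval is compared with a prespecified margin. The planned 90% confidence interval is compared with nothing.

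**Working it through.** **1. Estimability.** The response is change from baseline at Weeks 2 and 6. Subjects with topography: 18 + 18 = 36 assigned to VLN, 0 assigned to UB. At week *w* the pooled contrast is

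½(μ[VLN non-menthol, *w*] + μ[VLN menthol, *w*]) − ½(μ[UB non-menthol, *w*] + μ[UB menthol, *w*]).

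Both UB cells are empty. In the fixed-effects design of SAP 7.3 (group, week, group by week), adding any of the three contrast rows raises the rank of the design matrix, so none is estimable at either week. That is 3 contrasts × 2 weeks × 5 parameters = 30 rows, which is all of Table 14.2.3.3. VLN menthol against VLN non-menthol is estimable. The Week -1 UB sessions do not help: they are the VLN subjects' own baseline and are already subtracted from the response.

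**2. The plan's own figure.** The stated n=12 per group can be neither reproduced nor refuted, because no effect size or SD is given. Solving the noncentral-t power equation for a two-sided paired test at 0.05, n=12 and 80% power gives an implied effect of 0.889 SD of the paired differences. All SD units below are of this kind and are an assumption.

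**3. What non-significance would leave open.** P(non-significant) = P(|T| ≤ t(0.975, n−1)), where T is noncentral t with n−1 df and noncentrality δ√n.

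| Pairs | True shift 0.889 SD missed | True shift 0.5 SD missed |
|---|---|---|
| 36 (both flavours) | 0.06% | 17% |
| 30 (assumed per-protocol loss) | 0.3% | 25% |
| 24 (assumed per-protocol loss) | 1.4% | 35% |
| 18 (one flavour) | 5.6% | 48% |

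A true shift of 0.3 SD is missed 58% of the time at n=36. At n=36 the largest observed shift that is still non-significant is t(0.975, 35)/√36 = 2.030/6 = 0.338 SD. Its upper 90% limit is (2.030 + 1.690)/6 = 0.620 SD.

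**4. What a margin rule would need.** With true change zero and 80% power, the smallest workable margins are:

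| Pairs | Directional (one 90% CI limit inside the margin) | Two-sided (whole 90% CI within ± margin) |
|---|---|---|
| 36 | 0.42 SD | 0.50 SD |
| 30 | 0.47 SD | 0.55 SD |
| 24 | 0.52 SD | 0.62 SD |
| 18 | 0.61 SD | 0.72 SD |

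If a 95% limit were used instead, the directional margin at n=36 would be 0.48 SD.

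**5. The only estimable between-group comparison.** For VLN menthol against VLN non-menthol, 18 against 18, two-sided 0.05, 80% power is reached only at about 0.96 SD of the individual changes.

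**The case against.** **The defect produces a gap, not a wrong answer.** The paired test comes first in SAP 7.3, is feasible, carries its own primary label, and is the comparison topography was sized for. The mixed model is introduced as an addition, and SAP 14 warns that its shells may not fit every aspect of the study. This stands. The shell caveat does not reach the text of SAP 7.3, though, which applies the contrasts to topography.

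**No unrecorded major change is shown.** A reader might infer that the SAP promoted a new primary analysis without the amendment that protocol 6 requires for major modifications. The documents do not establish this. Protocol 6.3.7 already places a between-cohort model, topography included, under the primary endpoints. Protocol 6.1.1 already foresees between-group comparison of consumption, although as a secondary objective. The closing sentence of SAP 7.3 can also be read as choosing the pooled contrast over the two flavour-specific ones, just as the paired analysis selects the combined VLN group.

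**Nobody says p>0.05 means no compensation.** A reader might infer that the plan will draw that conclusion. No passage does: the objective is only to characterize behaviour, the hypothesis is an expectation with no decision rule, and the estimate and interval are reported whatever the p-value. No passage excludes the reading either, so one clarifying sentence is justified.

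**The SD figures are not anchored to this trial.** This is correct. The documents give neither an SD nor a meaningful change for any parameter, so the figures show a range and do not measure a known loss.

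**Conclusion.** SAP 7.3 is wrong as written for topography. All three VLN-versus-UB contrasts, including the one labelled primary, are non-estimable at both weeks, and Table 14.2.3.3 cannot be filled. This follows from the assignment text alone and needs no numerical assumption.

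It does not follow that topography lacks a valid primary analysis, because the paired test in the combined VLN group serves, or that any estimate is biased.

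The second part is conditional. If a non-significant paired test were offered as evidence of no compensation, it would be weak evidence against moderate shifts (17% missed at 0.5 SD and 58% at 0.3 SD with n=36), while shifts as large as the implied design effect would rarely be missed. These figures assume normal paired differences and SD units that the documents do not supply; n=24 and n=30 are illustrative losses.

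**What to change.** - **SAP 7.3:** exclude topography from the VLN-versus-UB contrasts and from the second primary-analysis sentence. Keep them for consumption, for biomarkers (SAP 8.4) and for subjective effects. SAP 10.3 reuses the same model and the between-group tables in SAP 14.2.9 depend on it, so restricting the contrasts to consumption would go too far.
- **Primary topography analysis:** name the paired Week 6 minus Week -1 change in the pooled VLN topography subset.
- **Table 14.2.3.3:** delete it. Alternatively, redesign it for VLN menthol against non-menthol if that is kept as the between-cohort comparison of protocol 6.3.7, labelled descriptive in view of its power.
- **Paired-comparison shells:** remove the UB-group rows for topography (Tables 11-5 and 14.2.3.2) and PK (Tables 11-21 and 14.2.7.11); the PK subset is also VLN only.
- **SAP 12:** note the clarification.
- **Interpretation:** state that p>0.05 will not be read as no compensation. If that conclusion is wanted, fix a margin for each parameter in advance and require the 90% interval to exclude it. The margin should be directional, with the direction of compensation stated, or two-sided if no change either way is claimed.
- **Separately, the code:** set alpha=0.10 in the PROC TTEST statement. The code sets no level, and the procedure's default interval is 95%, not the 90% the text promises. This affects consumption as well.

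The cost is wording, one table, some shell rows and one code option, with no new data or visits. Margins take work only if the stronger conclusion is sought, and some parameters may then be inconclusive if margins are tighter than about 0.42 SD (directional) or 0.50 SD (two-sided) at n=36.

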4. SAMPLE SIZE ESTIMATION

4.1 Cigarette Consumption

An intended sample size of 50 subjects in each of the two groups who switch from smoking usual brand to VLN cigarettes has been set for this study. This is based on powering the primary objective of a within-group comparison of cigarette consumption at baseline and end-of-study. The calculation was based on the number of pairs required to perform a one-tailed paired t-test with 80% power and an alpha level of 0.05 for a decrease in cigarette consumption of 3 CPD compared to available historical consumption data. The sample size was determined to be adequate based on potential non-compliance with the use of VLN cigarettes. A lower number (20) of smokers will be randomized to the continue-to-smoke usual brand groups, given the lower variability in consumption data and lower non-compliance anticipated in these groups. This will provide sufficient power for the secondary objective of between-group comparisons in cigarette consumption.

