8.4 Statistical Analysis of Biomarkers of Exposure

Paired t-tests will be used to compare urinary NNAL, NNN, 3-HPMA, S-PMA, 1-OHP, Tneq mass excreted, and blood COHb measures at the Week 2 and 6 time points with the baseline (Week -1) values. This analysis will be conducted on the evaluable subjects in the PP population. If data are unexpectedly found not to be normally distributed, an appropriate non-parametric test will be performed.

Differences will be considered statistically significant at an alpha level of 0.05. The same SAS codes used in [Section 7.3](#) for paired t-test will be used for the analysis.

In addition, a linear mixed model analysis of variance will be used to compare the between product group differences in the absolute change from baseline values of each of the urinary and blood BoEs. The same statistical model and SAS codes used in [Section 7.3](#) for product group comparisons will be used for the analysis.

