10.3 Statistical Analysis of Subjective Effects

Paired t-tests will be used to compare subjective effects measures at the Week 2 and 6 time points with the baseline (Week -1) values. This analysis will be conducted on the evaluable subjects in the PP population. If data are unexpectedly found not to be

normally distributed, an appropriate non-parametric test will be performed. Differences will be considered statistically significant at an alpha level of 0.05. The same SAS codes used in [Section 7.3](#) for paired t-test will be used for the analysis.

In addition, a linear mixed model analysis of variance will be used to compare the between product group differences in the absolute change from baseline values of each of the urinary and blood BoEs. The same statistical model and SAS codes used in [Section 7.3](#) for product group comparisons will be used for the analysis.

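### SAP 7.3 compares VLN with UB on change from Week -1 without the Week -1 value as a covariate, so the only concurrent-control comparison is usually less precise than the data allow

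*SAP*

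**What the plan says.** SAP 7.3 adds a linear mixed model to the paired t-tests, to "compare the between product group differences in the absolute change from baseline values of the consumption and puffing topography parameters". The text says "Product group, week, and product group by week interaction will be the fixed factors in the model", and the code agrees: "Model response = product_group week product_group*week /ddf=kr". No Week -1 term appears in either. Protocol 6.3.7 also plans a mixed model on absolute change and names no covariate.

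On status, SAP 7.3 says after the mixed-model code that "The primary analysis will be the pairwise comparisons of VLN combined versus UB combined", and identifies these as the flavour-pooled groups. Earlier in the same section it also calls the paired test in the combined VLN group primary. SAP 4.1 treats between-group comparison as secondary: "This will provide sufficient power for the secondary objective of between-group comparisons in cigarette consumption". It gives no effect size, SD or power for that comparison.

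The model is reused. SAP 8.4 applies it to biomarkers ("The same statistical model and SAS codes used in" Section 7.3). The sentence in SAP 10.3, on subjective effects, says it will "compare the between product group differences in the absolute change from baseline values of each of the urinary and blood BoEs", which names the biomarkers. Tables 14.2.9.1.3 to 14.2.9.4.3 nevertheless apply the between-group comparison to the subjective scores.

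**The concern.** The paired tests are within-group, so this mixed model is the only planned comparison with subjects followed over the same weeks on their usual brand. Only 40 of the 140 subjects are in that control, so precision matters.

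Subtracting Week -1 amounts to fixing the slope of follow-up on Week -1 at 1. If the true slope is smaller, the change score over-corrects. With equal SDs and correlation r, a chance Week -1 difference of 1 CPD between the arms leaves (1 - r) CPD of opposite sign in the contrast, which is 0.5 to 0.2 CPD for r of 0.5 to 0.8. Over repeated randomisations this averages to zero, but it adds noise that a covariate would remove. Week -1 consumption is recorded in every subject before allocation, so the covariate is already available. No baseline-adjusted sensitivity analysis is planned.

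**Working it through.** **Inputs.** Planned numbers are 50 VLN and 20 UB per flavour, so 100 against 40 combined. Sample-size settings are 3 CPD, 80% power and alpha 0.05, two-tailed in protocol 6.1.1 and one-tailed in SAP 4.1. Assumed, because the documents are silent: r of 0.5 to 0.8, and the SDs below.

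**The plan's own figure.** The 50 per VLN group cannot be reproduced without an SD. Inverting the paired t-test gives an SD of change of 7.42 (two-tailed) or 8.41 (one-tailed). These are upper bounds if part of the 50 allows for non-compliance.

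**Planned contrast.** With 7.42 in all groups, SE = 7.42 x sqrt(1/100 + 1/40) = 1.39. The 95% half-width is 2.75 CPD and the difference detectable at 80% power is 3.92 CPD.

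**Large-sample gain, one common slope.** With k = follow-up SD / Week -1 SD, the variance ratio (adjusted / change score) is (1 - r²)k² / (1 + k² - 2rk).
- k = 1: 0.75 (r = 0.5) and 0.90 (r = 0.8).
- k = 0.75: 0.52 to 0.56.
- k = 1.25: 0.89 to 1.00. At r = 0.8 the slope rk is 1, so there is no gain.

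**Simulated ratios at 50/50/20/20** (20,000 trials each, true difference -3, all estimators averaging -3.0). The unequal-slope rows assume Week -1 SD 8 and residual SD 4 (VLN) and 2 (UB).

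| Case | Common slope | VLN and UB slopes | Four slopes |
|---|---|---|---|
| Equal slopes, r = 0.5 | 0.748 | 0.752 | 0.771 |
| Equal slopes, r = 0.8 | 0.900 | 0.907 | 0.930 |
| Slopes 0.5 / 0.95 | 1.046 | 0.838 | 0.848 |
| Slopes 0.5 / 1.0 | 1.147 | 0.890 | 0.900 |
| Slopes 0.6 / 0.9 | 0.905 | 0.801 | 0.813 |
| Slope 1 in all groups | 1.008 | 1.015 | 1.043 |

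A second simulation gave 0.78 and 0.93 for four slopes in the first two rows.

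**Why a common slope can lose.** Take slopes 0.5 and 1.0.
- Change score: (0.5² x 64 + 16)/100 + (0 + 4)/40 = 0.320 + 0.100 = 0.420.
- Common slope, (100 x 0.5 + 40 x 1.0)/140 = 0.643: (0.143² x 64 + 16)/100 + (0.357² x 64 + 4)/40 = 0.173 + 0.304 = 0.477. Ratio 1.14.
- Separate slopes: 16/100 + 4/40 + 0.5² x 64/140 = 0.374. Ratio 0.89.

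**Why the default interval can be too short.** In the last line, the term (slope difference)² x 64/140 comes from estimating the baseline mean. A model interval evaluated at the sample mean treats that mean as known and omits the term. With residual SD 4 in both arms the retained part is 16/100 + 16/40 = 0.56. Approximate coverage is that of ±1.96 x sqrt(0.56 / total).

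| Slopes | Omitted term | Total | Approximate coverage | Simulated, four slopes |
|---|---|---|---|---|
| 0.5 / 1.0 | 0.114 | 0.674 | 0.926 | 0.930 |
| 0.5 / 0.95 | 0.093 | 0.653 | 0.930 | 0.931 |
| 0.6 / 0.9 | 0.041 | 0.601 | 0.942 | 0.937 |

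The variance ratios in these three cases were only 0.97, 0.92 and 0.92. A repeat simulation gave coverage of 0.925 to 0.938. The omitted term does not depend on having four slopes, so two slopes have the same problem.

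**In CPD, VLN and UB slopes, equal slopes, SD 7.42.** The half-width falls from 2.75 to 2.75 x sqrt(0.752) = 2.38 (r = 0.5) or 2.75 x sqrt(0.907) = 2.62 (r = 0.8). The detectable difference falls from 3.92 to 3.40 or 3.73.

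**The case against.** The planned contrast is unbiased under random allocation, follows protocol 6.3.7, and supplements a study sized on the within-group test. The gain cannot be fixed from the documents and may be small: at r of 0.7 to 0.9 the interval narrows by 1 - sqrt(0.85) = 7.8% down to 1 - sqrt(0.95) = 2.5%. The CPD figures apply the VLN-based SD to UB, although SAP 4.1 justifies the smaller UB groups as "given the lower variability in consumption data and lower non-compliance anticipated in these groups". A careless fix can also do harm, through a common slope or through an interval that under-covers. All of this stands. It limits the priority and shapes the fix, but it does not remove the omission.

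Three stronger readings are tempting and are not supported.

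- **That the unadjusted contrast is biased.** The protocol's design statement says non-randomized, but both documents describe random selection to VLN or UB within flavour, so its expectation is correct.
- **That the covariate would repair per-protocol selection.** The tables use the PP set, and the cotinine/CPD rule removes VLN subjects after switching. Simulations of the 0.2 cut-off (assumed median cotinine ratio 0.10, log-SD 0.6, about 25% of VLN subjects excluded) do not bear this out. Under an additive model the contrast was -3.05 in the full set, -1.79 in the PP change score and -1.83 after adjustment. The covariate recovered 0.04 of 1.26, about 3%. Under a multiplicative model the figures were -2.50, -1.72 and -1.72.
- **That the SAP defines the pooled groups only for the paired test.** Section 7.3 names the pooled comparison directly after the mixed-model code, and the table shells carry its row. What is missing is code that outputs it: the printed LSMEANS statement on the four groups does not.

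**Conclusion.** The omission is explicit in text and code. The comparison remains valid but is usually less precise than the collected data allow. For consumption, with r of 0.5 to 0.8, equal SDs and equal slopes, the variance saving is about 25% to 10% with a common slope and about 22% to 7% with four slopes. It is near zero, or a loss of about 4% with four slopes, when the true slope is near 1. The correlation, SDs and slopes are all assumptions. No figure is claimed for biomarkers or subjective scores, where the same reasoning applies but the size is unknown. This is a cheap improvement worth making; it does not correct an invalid analysis.

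**What to change.** Apply the following to endpoints measured in both VLN and UB subjects.

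1. Keep the four-level product group and the change-score response. Add the Week -1 value centred at its mean in the analysis set (`base_c`): `base_c`, `base_c*week`, `base_c*arm` and `base_c*arm*week`, with `arm` being VLN or UB. Two slopes per week are enough. Do not use one common slope at 100:40.
2. Compute a standard error that allows for the estimated baseline mean and for unequal variances. One way is a bootstrap of subjects within product group that recentres `base_c` in each resample. Its coverage was not simulated here, so check it before database lock.
3. Add an ESTIMATE or LSMESTIMATE for VLN combined against UB combined at Week 2 and at Week 6, at `base_c` = 0. State whether flavours are weighted equally (1/2, 1/2, -1/2, -1/2) or by subject numbers. The two agree at the planned sizes but not in an analysis set with unequal flavour groups.
4. Do not apply the model to topography (Table 14.2.3.3). SAP 7.1.3 measures only VLN-assigned subjects.

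**Cost.** No new data, and four slope parameters (two arms by two weeks). With equal slopes, two slopes cost under 1% in variance against a common slope (0.752 against 0.748; 0.907 against 0.900). The loss is about 1.5% if the slope is 1 everywhere. Record the change in SAP 12. Protocol 6 lets the SAP modify the outlined plan but requires an amendment for major modifications of the primary endpoints or their analysis, so the sponsor must decide whether this is one.
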